#### **5.6.2 Prohibited concomitant therapy**

Concomitant use of sargramostim (GM-CSF), other anti-cancer therapies, including radiation, thalidomide, or other investigational agents is not permitted while subjects are receiving study drug during the treatment phase of the study.

## 5.7 Discontinuation of Study Treatment

Treatment will continue until the occurrence of any of the following events.

- Disease progression as defined in Appendix C
- Adverse event(s) that, in the judgment of the Investigator, may cause severe or permanent harm or which rule out continuation of the treatment regimen.
- Discontinuation of lenalidomide for any reason.
- Major violation of the study protocol.
- Withdrawal of consent
- Lost to follow up
- Death
- Pregnancy
- Patient requests to be removed from study

## 5.8 Follow-Up

Subjects who discontinue treatment for any reason will not be followed. At treatment discontinuation, subjects will undergo a safety assessment approximately 28 days post the last dose of study drug. In addition, off study evaluations per the Schedule of Assessments, Section 2 will be done. All subjects who respond to treatment will be followed for survival indefinitely.

## 6 Adverse events

### 6.1 Serious Adverse Event (SAE) Definition

A serious adverse event is one that at any dose (including overdose):

- Results in death
- Is life-threatening
- Requires inpatient hospitalization or prolongation of existing hospitalization
- Results in persistent or significant disability or incapacity
- Is a congenital anomaly or birth defect
- Is an important medical event

“Life-threatening” means that the subject was at immediate risk of death at the time of the serious adverse event; it does not refer to a serious adverse event that hypothetically might have caused death if it were more severe.

“Persistent or significant disability or incapacity” means that there is a substantial disruption of a person’s ability to carry out normal life functions.

Medical and scientific judgment should be exercised in deciding whether expedited reporting is appropriate in situations where none of the outcomes listed above occurred. Important medical events that may not be immediately life-threatening or result in death or hospitalization but may jeopardize the patient or may require intervention to prevent one of the other outcomes listed in the definition above should also usually be considered serious. Examples of such events include allergic bronchospasm requiring intensive treatment in an emergency room or at home, blood dyscrasias or convulsions that do not result in inpatient hospitalization, or the development of drug dependency or drug abuse. A new diagnosis of cancer during the course of a treatment should be considered as medically important.

## 6.2 Adverse Drug Reaction Reporting

Toxicity will be scored using CTCAE Version 3.0 for toxicity and adverse event reporting. A copy of the CTCAE Version 3.0 can be downloaded from the CTEP homepage ([HTTP://CTEP.INFO.NIH.GOV](http://CTEP.INFO.NIH.GOV)). All appropriate treatment areas should have access to a copy of the CTCAE Version 3.0. All adverse clinical experiences, whether observed by the investigator or reported by the patient, must be recorded, with details about the duration and intensity of each episode, the action taken with respect to the test drug, and the patient’s outcome. The investigator must evaluate each adverse experience for its relationship to the test drug and for its seriousness.

The investigator must appraise all abnormal laboratory results for their clinical significance. If any abnormal laboratory result is considered clinically significant, the investigator must provide details about the action taken with respect to the test drug and about the patient’s outcome.

SPMs are considered events of interest and should be included as part of the assessment of adverse events throughout the course of the study. Investigators are to report any second primary malignancies as serious adverse events regardless of causal relationship to lenalidomide, occurring at any time for the duration of the study. For all subjects who develop second primary malignancies, sites will be required to submit all diagnostic reports (eg pathology, cytogenetics, flow cytometry results) from the indication diagnostic confirmation samples submitted at screening and all reports for the tumor samples from the SPM diagnosis. For SPMs diagnosed at another institution (outside the

investigational site), sites are to make every effort to obtain these reports for the SPM confirmation.

### 6.2.1 Pregnancies

Pregnancies and suspected pregnancies (including a positive pregnancy test regardless of age or disease state) of a female subject occurring while the subject is on lenalidomide or within 28 days after the subject's last dose of lenalidomide are considered immediately reportable events. If the subject is on lenalidomide, it is to be discontinued immediately and the subject is to be instructed to return any unused portion of lenalidomide to the Investigator. The pregnancy must be reported to Celgene Drug Safety immediately of the Investigator's knowledge of the pregnancy by phone and facsimile using the Pregnancy Initial Report Form.

The Investigator will follow the subject until completion of the pregnancy, and must notify Celgene Drug Safety immediately about the outcome of the pregnancy (either normal or abnormal outcome) using the Pregnancy Follow-up Report Form. If the outcome of the pregnancy was abnormal (e.g., spontaneous or therapeutic abortion), the Investigator should report the abnormal outcome as an AE. If the abnormal outcome meets any of the serious criteria, it must be reported as an SAE to Celgene Drug Safety immediately by facsimile, or other appropriate method, within 24 hours of the Investigator's knowledge of the event using the SAE Report Form,

All neonatal deaths that occur within 28 days of birth should be reported, without regard to causality, as SAEs. In addition, any infant death after 28 days that the Investigator suspects is related to the *in utero* exposure to lenalidomide should also be reported to Celgene Drug Safety immediately by facsimile, or other appropriate method, within 24 hours of the Investigator's knowledge of the event using the SAE Report Form.

### Male Subjects

If a female partner of a male subject taking investigational product becomes pregnant, the male subject taking lenalidomide should notify the Investigator, and the pregnant female partner should be advised to call their healthcare provider immediately.

**[contact]**  
**E-mail: [[contact]](mailto:[contact])**

### 6.3 Investigator Reporting Responsibilities

The conduct of the study will comply with all FDA safety reporting requirements.

#### IND Annual Reports

If the FDA has granted an IND number, it is a requirement of 21 CFR 312.33, that an annual report is provided to the FDA within 60-days of the IND anniversary date. 21 CFR 312.33 provides the data elements that are to be submitted in the report. The Annual Report should be filed in the study's Regulatory Binder (or some such phrase), and a copy provided to Celgene Corporation as a supporter of this study as follows.

Celgene Corporation  
Attn: Medical Affairs Operations  
Connell Corporate Park  
[name]  
[name]

All adverse experience reports must include the patient number, age, sex, weight, severity of reaction (mild, moderate, severe), relationship to study drug (probably related, unknown relationship, definitely not related), date and time of administration of test medications and all concomitant medications, and medical treatment provided. The investigator is responsible for evaluating all adverse events to determine whether criteria for "serious" and as defined above are present. The investigator is responsible for reporting adverse events to Celgene as described below.

#### 6.3.1 Expedited reporting by investigator to Celgene

Serious adverse events (SAE) are defined above. The investigator must inform Celgene in writing using a Celgene SAE form or MEDWATCH 3500A form of any SAE within 24 hours of being aware of the event. The written report must be completed and supplied to Celgene by facsimile within 24 hours/1 business day at the latest on the following working day. The initial report must be as complete as possible, including an assessment of the causal relationship between the event and the investigational product(s), Information not available at the time of the initial report (e.g., an end date for the adverse event or laboratory values

received after the report) must be documented on a follow-up report. A final report to document resolution of the SAE is required. The Celgene tracking number (RV-PI-MM-0345), and the institutional protocol number, and the patient ID number should be included on SAE reports (or on the fax cover letter) sent to Celgene. A copy of the fax transmission confirmation of the SAE report to Celgene should be attached to the SAE and retained with the patient records.

Any SAEs incurred at subsites must be reported immediately to the VA BOSTON office **and** to Celgene within 24 hours/1 business day at the latest on the following working day of awareness of the event.

### **6.3.2 Report of Adverse Events to the Institutional Review Board**

The principal Investigator is required to notify his/her Institutional Review Board (IRB) of a serious adverse event according to institutional policy.

### **6.3.3 Investigator Reporting to the FDA**

**Serious** adverse events (SAEs) that are **unlisted/unexpected, and at least possibly associated to the drug**, and that have not previously been reported in the Investigators brochure, or reference safety information document should be reported promptly to the Food and Drug Administration (FDA) by telephone or by fax. Fatal or life threatening SAEs that meet the criteria for reporting to the FDA must be reported to the FDA within 7 calendar days after awareness of the event. All other SAEs that meet the criteria for reporting to the FDA must be reported to the FDA within 15 calendar days after awareness of the event. A clear description of the suspected reaction should be provided along with an assessment as to whether the event is drug or disease related.

Participating study sites should NOT report SAEs to the FDA. Participating sites should report SAEs to Celgene and the VA Boston site, and the VA Boston site will be responsible for reporting to FDA.

## **6.4 Adverse event updates/IND safety reports**

Celgene shall notify the Investigator via an IND Safety Report of the following information:

- Any AE associated with the use of study drug in this study or in other studies that is both serious and unexpected.
- Any finding from tests in laboratory animals that suggests a significant risk for human subjects including reports of mutagenicity, teratogenicity, or carcinogenicity.

The Investigator shall notify his/her IRB/EC promptly of these new serious and unexpected AE(s) or significant risks to subjects.

The Investigator must keep copies of all AE information, including correspondence with Celgene and the IRB/EC, on file (see Section 11.4 for records retention information).

## **7 Response Criteria**

Efficacy assessments are scheduled to occur on day 1 of each even cycle (cycle 2, 4, 6, etc.).

All partial and complete responses must be confirmed with another efficacy assessment in no less than 4 weeks apart.

Response and progression will be evaluated in this study using the EBMT and IMWG criteria

Instructions for interpreting response criteria and best overall response may be found in Appendix C: Response Evaluation Criteria.

## **8 Protocol Amendments/Deviations**

### **8.1 Protocol amendments**

Any amendment to this protocol must be agreed to by the Principal Investigator and reviewed by Celgene. Amendments should only be submitted to IRB/EC after consideration of Celgene review. Written verification of IRB/EC approval will be obtained before any amendment is implemented.

### **8.2 Protocol deviations**

When an emergency occurs that requires a deviation from the protocol for a subject, a deviation will be made only for that subject. A decision will be made as soon as possible to determine whether or not the subject (for whom the deviation from protocol was effected) is to continue in the study. The subject's medical records will completely describe the deviation from the protocol and state the reasons for such deviation. In addition, the Investigator will notify the IRB/EC in writing of such deviation from protocol.

Non-emergency minor deviations from the protocol will be permitted with approval of the Principal Investigator.

## 9 Study Monitoring and Auditing

### 9.1 Investigator responsibilities

Investigator responsibilities are set out in the ICH guideline for Good Clinical Practice (GCP) and in the US Code of Federal Regulations.

Investigators must enter study data onto CRFs or other data collection system. The Investigator will permit study-related monitoring visits and audits by Celgene or its representatives, IRB/EC review, and regulatory inspection(s) (e.g., FDA, EMEA, TPP), providing direct access to the facilities where the study took place, to source documents, to CRFs, and to all other study documents.

The Investigator, or a designated member of the Investigator's staff, must be available at some time during monitoring visits to review data and resolve any queries and to allow direct access to the subject's records (e.g., medical records, office charts, hospital charts, and study related charts) for source data verification. The data collection must be completed prior to each visit and be made available to the Celgene representative so that the accuracy and completeness may be checked.

## 10 Biostatistical Analysis

### 10.1 Overview

This is a multi-center, controlled, open-label, randomized, parallel group study intended to select a tolerable dose regimen with acceptable efficacy of lenalidomide, when used in combination with dexamethasone. Patients will be randomized with 1:1 ratio to receive lenalidomide 25 mg + dexamethasone or lenalidomide 15mg + dexamethasone. The primary objective of the study is to evaluate the frequency of dose reductions in two different lenalidomide dose regimens. The study will help in selecting a safe lenalidomide dose for the elderly population.

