### 3.3 Rationale

The primary rationale is to utilize Revlimid at dose that will be well tolerated and effective. We propose to use the need for dose reduction as a criterion to judge tolerability from various causes. In the veteran population which predominantly is in the older age category with number of co-morbidities, a lower dose regimen may be safer and advantageous. In a recent multi-institutional study, the 009 and 010 studies, patients were randomized to receive Revlimid with dexamethasone versus dexamethasone alone. A logistic regression was performed using dose reduction (i.e., whether or not having any lenalidomide dose reduction as the dependent variable). Treatment-emergent neutropenia and thrombocytopenia were the causes of the majority of dose reductions. Predictors analyzed included: age, prior transplant (yes vs. no), high vs. low risk (disease stage variable), previous thalidomide exposure (yes vs. no), previous lines of therapy (<=2 vs. 3+), prior medical history of neutropenia or thrombocytopenia. Among the 353 patients in the Revlimid/Dexamethasone groups, 131 (37.1%) had at least one dose reduction of Revlimid. Age, whether used as a continuous variable or dichotomized one (<=65 vs. 66+), was the single significant predictor for dose reduction; 46% of the patients aged 66 or older required at least one dose reduction, as compared to 31% of the patients aged 65 or younger. Of

interest, when the elderly population was specifically examined, the outcomes were similar for response rate, time to progression and overall survival than the younger group, suggesting that dose reduction had no significant effect on efficacy.

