**Other: symptomatic hyperviscosity, amyloidosis, recurrent bacterial infections (> 2 episodes in 12 months)**

**5.2.1.1** Patients must have relapsed or refractory disease (refractory is defined as progression during treatment or within 60 days after the completion of treatment) requiring 2nd or 3rd line therapy (see Appendix C)

**5.2.1.2** Patients may have received lenalidomide and/or dexamethasone

**5.2.1.3** Patients with measurable disease defined as:

- Serum monoclonal protein > 0.5 g/dL and/or 0.2 g/24hr urine light chain excretion
- Patients with lower M-protein values or non-secretory myeloma will be eligible if measurable disease can be established, such as serum Freelite™ chain ratio > 5x normal limit, measurable soft tissue plasmacytoma > 2 cm by either physical exam and/or applicable radiographs (i.e. MRI, CT-scan) and/or bone marrow involvement > 30%

- 5.2.1.4** Age  $\geq 18$  years at the time of signing the informed consent form.
- 5.2.1.5** All necessary baseline studies for determining eligibility must be obtained within 14 days prior to enrollment. Serum pregnancy tests (sensitivity of at least 50 mIU/mL), for females of childbearing potential (WCBP) must be completed. The first test must be performed within 10-14 days, and the second test within 24 hours prior to initiation of lenalidomide.
- 5.2.1.6** Pre-study ECOG performance status 0-2. Patients with lower performance status based solely on bone pain will be eligible.
- 5.2.1.7** Patients must have adequate liver functions: AST and ALT  $\leq 3x$  upper limit of normal, alkaline phosphatase  $\leq 3.0x$  upper limit of normal, except if attributed to tumor, and bilirubin  $\leq 2 x$  upper limit of normal.
- 5.2.1.8** Patients must have amylase  $\leq 2.5x$  upper limit of normal
- 5.2.1.9** All study participants must be registered into the mandatory RevAssist® program, and be willing and able to comply with the requirements of RevAssist®.
- 5.2.1.10** Subject must be able to adhere to the study visit schedule and other protocol requirements
- 5.2.1.11** Subject must understand and voluntarily sign an informed consent document.

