## 5.4 Drug Administration

### 5.4.1 Treatment assignments

Subjects who qualify for the study will be randomized to either Lenalidomide 15 mg p.o. q.d. days 1-21 of a 28 day cycle or Lenalidomide 25 mg p.o. q.d. for days 1-21 of a 28 day cycle. In addition, dexamethasone (40mg) will be added once a week (Days 1, 8, 15, 22) to the lenalidomide regimen

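### The plan says the study will help choose a safe dose for the elderly, but it plans no estimate in patients aged 66 or older and lets age into the primary model only through a significance screen

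*Combined protocol and SAP*

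**What the plan says.** Section 10.1 gives the intended use of the result in one sentence: "The study will help in selecting a safe lenalidomide dose for the elderly population". Section 3.3 supplies the reasoning: "In the veteran population which predominantly is in the older age category with number of co-morbidities, a lower dose regimen may be safer and advantageous". It then reports, from the 009 and 010 trials, that age "was the single significant predictor for dose reduction", and that "46% of the patients aged 66 or older required at least one dose reduction, as compared to 31% of the patients aged 65 or younger". Across all 353 lenalidomide patients in those trials, "131 (37.1%) had at least one dose reduction of Revlimid".

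The design does not carry this through:

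- **Eligibility.** Criterion 5.2.1.4 sets the minimum age at 18 "years at the time of signing the informed consent form". There is no elderly threshold or quota, and Section 10 does not say what age counts as elderly.
- **Randomisation.** Section 10.1 says "Patients will be randomized with 1:1 ratio to receive lenalidomide 25 mg + dexamethasone or lenalidomide 15mg + dexamethasone", and Section 5.4.1 says "Subjects who qualify for the study will be randomized to either Lenalidomide 15 mg" or the 25 mg regimen. Neither names a stratification factor. Section 10.3 does speak of stratifying, but it means splitting each arm after randomisation by whether a dose reduction occurred.
- **Model.** Section 10.3 compares demographic variables across the four arm-by-reduction groups. Only those that differ significantly become covariates in the logistic model, and the Cox analysis uses the same set if necessary. Age is not named in either model.
- **Elderly result.** Sections 10.2 to 10.5 plan no estimate by age.

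**The concern.** Dose reduction is the primary outcome variable in Section 10.3, and the protocol has already identified one factor known to predict it, with a ready cut-point at 66. The plan then commits to no use of that factor. Two things follow.

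First, every planned result pools all adults, so a reader who wants to apply the finding to older patients, as Section 10.1 invites, has no figure for them and no view of how precise such a figure would be.

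Second, whether age is adjusted for depends on a test in the trial's own data. Because the four groups are formed partly by the outcome, the adjustment set depends on the outcome as well. In 80 patients, a test of this kind can easily miss a factor that is genuinely prognostic.

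**Working it through.** **Inputs.** 40 patients per arm, 50% vs 20% (Section 10.5); two-sided 0.05 (Section 10.3); 46%, 31% and 37.1% (Section 3.3).

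**1. The plan's own power figure.** Pooled-variance normal approximation with 40 per arm:

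- Null standard error = √(2 × 0.35 × 0.65 / 40) = 0.1067.
- Alternative standard error = √((0.5 × 0.5 + 0.2 × 0.8) / 40) = 0.1012.
- Power = Φ((0.30 − 1.96 × 0.1067) / 0.1012) = 81.6%.

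This matches Section 10.5. It applies to all 80 patients, not to an elderly subset.

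**2. Elderly share.** The documents give none for this trial, so it is an assumption. The 009/010 rates imply (37.1 − 31) / (46 − 31) = 0.41 aged 66+, or about 0.37 to 0.44 allowing for rounding of the two age-specific rates. Section 3.3 describes veterans as mostly older, so the share here may be higher. A range is therefore shown.

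**3. What the 66+ subset could show.** The formula in step 1 is applied with n = 40 × share per arm, keeping 50% vs 20%. The half-width is 1.96 × √(0.41 / n).

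| Assumed share 66+ | Per arm | Power | 95% CI half-width |
|---|---|---|---|
| 40% | 16 | 42% | 31 points |
| 50% | 20 | 51% | 28 points |
| 70% | 28 | 66% | 24 points |
| 80% | 32 | 72% | 22 points |
| 100% | 40 | 82% | 20 points |

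**4. Would age pass the screen?** As an approximation, compare 46% with 31% in 80 patients divided by age. Power is about 28% at a 40% or 50% share, 26% at 60% and 23% at 70%; at 80% it is lower still, about 18%. The planned screen is not this test. It uses four groups, with a two-way analysis of variance if age is kept continuous, so these figures indicate the order of size only. They suggest that age would more likely than not be left out, even if its effect is as large as in 009/010.

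**5. Chance imbalance without stratification.** The standard deviation of the between-arm difference in the 66+ share is √(2p(1 − p) / 40): 0.110 at p = 0.41, 0.102 at 0.70 and 0.089 at 0.80. The chance of a difference of 15 points or more is about 17%, 14% and 9% respectively, with a maximum of 18% at p = 0.50.

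**6. Consequence of that imbalance.** A 15-point imbalance shifts the crude difference by 0.15 × (46 − 31) = 2.25 points. The planned difference is 30 points, with a standard error of about 10 points (step 1).

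**7. Precision gained from age.** The share of outcome variance explained by the age split is 0.407 × 0.593 × 0.15² / (0.371 × 0.629) = 0.0054 / 0.233 = 2.3%. Removing it entirely would reduce the standard error by 1 − √(1 − 0.023), about 1.2%.

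**The case against.** The strongest reply is that the elderly are not the trial's stated target. They do not appear in the title, the primary or secondary objectives, or the eligibility criteria, and Section 10.1 says only that the study will help in the choice. That is fair. A reader might infer that the trial's main aim is to choose a dose for the elderly and that the design fails that aim; the documents do not support so strong a reading. What remains is a sentence about applicability with no analysis behind it, and rewording alone would remove the mismatch.

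It can also be said that the sample will be mostly elderly anyway. Section 3.3 points that way, and the 50% rate assumed for the 25 mg arm lies above the 46% seen at 66 or older, which would fit planning for an older group, though the protocol does not say so. The more elderly the sample, the closer the pooled result comes to an elderly result. But nothing secures the share or requires it to be reported, and a larger share also makes the 66+ estimate more precise.

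Unstratified 1:1 allocation of 80 patients is valid, and steps 6 and 7 show that stratification would gain little. Nor can one say that randomisation ignores age: the text names no factor, but it says almost nothing about the allocation method, and the design figure in Section 5.1 is not available. An age-by-arm interaction in 80 patients would be barely informative, and this point does not ask for one.

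**Conclusion.** The concern holds as a gap between what Section 10.1 says and what Section 10 plans. The two parts that matter are the missing estimate in patients aged 66+ and the reliance on a weak, outcome-dependent screen to decide whether age is adjusted for. Both can be put right with data the trial will collect anyway.

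Three stronger conclusions should not be drawn. The primary comparison is not materially compromised: a sizeable age imbalance has a chance of about 9-18% at shares between 80% and 41%, but moves the result by only about 2 points against a planned 30. Low power in the 66+ subset is not in itself a defect, since the plan proposes no test there; the figures in step 3 show how cautiously an elderly estimate would have to be read. A reader might also suppose that a pooled difference could be driven by younger patients. That is possible, but nothing in the documents suggests a smaller dose effect in older patients, and the only age data given show more reductions among them.

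The sizes rest on an assumed elderly share of 40% to 80%, on the Section 10.5 rates applying within the 66+ subset, and on the 009/010 age effect carrying over to this trial.

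**What to change.** 1. In Section 10.3, enter age in the primary logistic model and the Cox model regardless of any screening test, and state its form in advance (for example, the cut at 65 or younger vs 66+ already used in Section 3.3).
2. Add a planned table of dose-reduction rates by arm in patients aged 66+, with the difference and its 95% CI, labelled as estimation and not as a powered test. Report the number aged 66+ in each arm beside it.
3. Limit the elderly sentence in Section 10.1 to what that estimate supports, and state the age cut that it refers to.
4. Optional, and only if randomisation has not begun: stratify the allocation by 65 or younger vs 66+. The gain is small.

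Items 1 to 3 need no new data and no more patients; they cost a few lines of text and a few table rows. Item 4 needs a two-stratum randomisation list. The drawback is that the 66+ estimate will be imprecise, with a half-width of roughly 22 to 31 points over the shares considered, and must be presented as such.
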